9.1 Blood Specimens

9.1.1 Collection of Specimens

Forty mL of blood will be collected into 4 pink top tubes (with EDTA) for isolation of PBMCs at the following time points **for Phase II patients only**:

- No more than one week prior to surgical procedure (including resection/debulking, MLA or biopsy)
- No more than 3 days prior to the first dose of MK-3475
- No more than 7 days prior to the second dose of MK-3475 and at doses 4, 6, 9, 18, and 36
- At the end of treatment visit

9.1.2 Handling of Specimens

One 10 mL vial will be used for isolation of plasma via centrifugation. The remaining vials will be used for isolation of peripheral blood mononuclear cells (PBMCs) using Ficoll per standard protocol^{37,38}.

9.1.3 Shipping of Specimens

Blood samples collected at WUSM should be transported to and stored in [name]'s lab (located at Couch Biomedical Research Building [name]) or the Siteman Cancer Center's Tissue Procurement Core (located on the 5th floor of the BJCIIH) at ambient temperature immediately after collection and processed immediately upon arrival. If a delay in transport or processing of greater than 1 hour is anticipated, samples must be stored on ice. All attempts must be used to process samples within 4 hours of collection.

Blood samples collected at UF should be transported to [name] lab to be processed within their immunophenotyping lab at ambient temperature immediately after collection and processed immediately upon arrival. If a delay in transport or processing of greater than 1 hour is anticipated, samples must be stored on ice. All attempts must be used to process samples within 4 hours of collection.

Preliminary processing of the scRNAseq samples will be completed by the MGI lab locally at WUSM. To ensure data analysis consistency, the resulting data will then be stripped of any identifying information and shared with UF, where it will be aggregated and analyzed as a cohort.

9.2 Cervical Lymph Node Samples - OPTIONAL

9.2.1 Collection of Specimens

Ipsilateral cervical lymph nodes of all phase II patients will be sampled by FNA (regardless of whether the node is pathologically enlarged) at the following time points:

- Time of surgical resection/debulking or biopsy or MLA/biopsy
- 6 weeks +/- 1 week after surgical resection/debulking or biopsy or MLA/biopsy (if tumor-specific precursor frequency in PBMC is low)

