1.6 Correlative Studies Background

In both arms of phase II, intratumoral PD-L1 expression will be determined by qRT-PCR and/or IHC. TIL profile will be assessed by flow and mass spectrometry or IHC to compare to the profile at initial surgery prior to recurrence (when available). Glioma-specific immune response will be assessed in cultured TIL, peripheral blood, and sampled cLN (where available). Pre- and post-surgery peripheral blood will be assessed by flow cytometry through the Center for Human Immunology and Immunotherapy immune monitoring core (for Washington University samples) and the [name] lab or the University of Florida Brain Tumor Immunotherapy Program (for the UF samples) for markers of T cell activation and anergy as well as cytokine profiles. In addition, PD-1-dependent signature in glioma cell-specific T cells from the peripheral blood and sampled cLN where samples and RNAseq are available can be generated by novel RNAseq methodology developed at Washington University and University of Florida in order to characterize the PD-1-dependent transcriptional signatures and develop a PD-1 dependent biomarker program that will be easily de-convoluted to provide data on serial changes in (a) cell type composition and (b) cell type activation programs. Furthermore, if necessary, serum or plasma will be assessed for the presence and level of soluble immune checkpoint molecules, cytokines, and chemokines using commercially available multiplex immunoassays.

1.7 Rationale for Amendment 12

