2.2 Secondary Objectives

1. Phase I: To determine the toxicity profile of MK-3475 in combination with MLA for the treatment of recurrent malignant gliomas.
2. Phase II: To determine the overall survival (OS) of patients with recurrent GBM, WHO grade IV being treated with MK-3475 plus MLA as compared to historical controls treated with MK-3475 alone.
3. Phase II: To assess the anti-glioma immune response before and after MK-3475 with MLA.
4. Phase II: To correlate intratumoral expression of PD-L1 and the frequency of glioma cell-specific cytotoxic T cells with PFS and OS.
5. Phase II: To identify PD-1-dependent biomarkers in glioma cell-specific T cells that negatively correlate with the frequency of glioma cell-specific cytotoxic T cells and PFS and OS.

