For all phase II patients, research blood will be drawn prior to MLA and immediately prior to the first dose of MK-3475. Subsequently, research blood will be drawn at doses 2, 4, 6, 9, 18, 36, and at the end of treatment. In addition, an optional ipsilateral cervical lymph node may be sampled by FNA prior to or at the time of surgical procedure (including surgical debulking, MLA, or biopsy) and again 6 weeks after surgery. Those patients who, in the event of surgical intervention for clinical reasons of a radiographically progressing tumor, undergo a subsequent surgical procedure (whether biopsy or resection) will have tissue collected for correlative analysis after histopathologic diagnosis of recurrent GBM.

Additionally, for patients enrolled to phase II who have surgical intervention for a radiographically progressing tumor but subsequent surgical pathology demonstrating a predominant immune-mediated reaction **with no obvious progression of tumor**, such subjects will be deemed not to have progressed and be allowed to resume assigned study treatment at a time deemed safe by the treating physician, but no later than 8 weeks from the surgery.

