10.2 Phase II Study Calendars

10.2.1 MK-3475 + MLA

	Screening	Surgical Resection/Debulking (OPTIONAL)	Day 1 (MLA) (no surgical resection / debulking) ¹⁵	Day 1 (MLA) (3 weeks post-surgical resection / debulking ¹⁶)	Day 2 to Day 9	Q3W ¹⁷	EOT ³
H&P, KPS	X				X ¹²	X	X
Brain MRI	X				X ²⁰	X ⁹	
CBC	X ¹⁸				X	X	
CMP ¹³	X ¹⁸				X	X	
INR, PT/PTT	X ¹⁸						
βhCG ¹¹	X ¹⁸				X ¹⁰		
TSH	X ¹⁸				X ²	X ²	
MK-3475					X ¹	X ⁴	
MLA			X ^{6, 15}	X ^{6, 16, 19}			
Surgical resection (optional)		X					
Biopsy			X ¹⁴				
Research blood		X ^{5,7}	X ^{5, 7}		X ⁵	X ⁵	X ⁵
Research lymph nodes		X ⁷	X ⁷			X ⁸	
Research tissue		X ⁷	X ⁷				
AE assessment	X						X ²¹

1. To begin no more than 1 week (+/- 3 days) after MLA or 3 weeks after surgery.
2. To be checked at the first MK-3475 dose and then every other dose thereafter
3. There will be one follow-up visit 4 weeks after EOT, and then patients will be followed for up to 2 years for survival
4. Patients currently on MK-3475 beyond the 2 year/35 cycle limit at the time of this amendment may remain on MK-3475 unless there is progression, toxicity or agreement by the patient and PI to come off therapy. The number of treatments is calculated starting with the first dose. Participants who stop the combination or MK-3475 after receiving 35 doses may be eligible for retreatment if they progress after stopping study intervention provided they meet the requirements detailed in Section 5.10. Participants may be retreated in the Second Course Phase (Retreatment) for up to an additional 17 cycles (approximately 1 year).
5. Refer to Section 9.1
6. Patients will receive peri- and post-operative care as per SOC. This typically includes treatment with steroids and anti-epileptics, repeated neurological exams (approx. hourly in the ICU and approx. every 2 hours in the step-down unit), and draws for CBC and CMP immediately post-MLA and again the following day.
7. At time of surgery
8. 6 weeks post-surgery only (+/- 1 week)
9. Every 9 weeks (+/- 1 week)
10. No more than 72 hours prior to the first dose only. Additional pregnancy tests are not required.
11. Women of childbearing potential only
12. One week +/- 2 days following MLA or on the first dose of MK-3475 (whichever comes first)
13. CMP consists of albumin, alk phos, ALT, AST, BUN, Ca++, Cl-, CO2, creatinine, glucose, K+, Na+, total bili, total protein.

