11.0 DATA SUBMISSION SCHEDULE

Case report forms with appropriate source documentation will be completed according to the schedule listed in this section.

Case Report Form	Submission Schedule
Original Consent Form	Prior to registration
Registration Form Eligibility Form Demographics Form Medical Record Number Form Participant Address Form On-Study Form On-Study Treatment History Form On-Study Surgical History Form	Prior to starting treatment
MK-3475 Dosing Form	With each dose of MK-3475 (during main study and second course as applicable)
MLA Form	Time of MLA
Surgery Form Treatment Assignment Form	Time of surgery
Research Nodes and Tissue Form (Phase II only)	Time of surgical procedure 6 weeks post-surgical procedure
Research Blood Form (Phase II only)	Prior to starting treatment Time of MLA Time of surgical procedure With each dose of MK-3475 (Per section 9.1)
Retreatment Form	Time of start of second course
Adverse Events Form	Continuous
Treatment Summary Form	Completion of treatment
Follow Up Form	Per protocol
Imaging Form	Baseline, every 9 +/- 1 weeks, and end of treatment
MedWatch Form	See Section 7.0 for reporting requirements

Any queries generated by Washington University must be responded to within 28 days of receipt by the participating site. The Washington University research team will conduct a regular review of data status at all secondary sites, with appropriate corrective action to be requested as needed.

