15.2 Analysis Plan

PFS and OS will be estimated by Kaplan-Meier product limit method and the difference in PFS with recurrent GBM being treated with MK-3475 alone vs. those being treated with MK-3475 plus MLA will be compared by log-rank test.

Two-group t-test will be used to compare the anti-glioma immune response before and after MK-3475 with or without MLA.

Cox proportional hazard model will be used to determine the relationship between intratumoral expression of PD-L1, the frequency of glioma cell-specific cytotoxic T cells with PFS and OS while proportional hazard assumption will be examined.

Pearson correlation coefficient (r) will be calculated between intratumoral expression of PD-L1 and the frequency of glioma cell-specific cytotoxic T cells. Similarly, Cox proportional hazard model will be used to investigate the relationship between PD-1-dependent biomarkers in glioma cell-specific T cells and PFS and OS.

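### Section 9.2.1 makes the optional 6-week lymph node depend on a low blood frequency while four other places do not; if 9.2.1 is followed, the node before/after comparison is biased by selection

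*Combined protocol and SAP*

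**What the plan says.** Section 9.2 is headed as optional. Within it, 9.2.1 states "Ipsilateral cervical lymph nodes of all phase II patients will be sampled by FNA (regardless of whether the node is pathologically enlarged") and gives two time points. The first, at the surgical procedure, carries no condition. The second, 6 weeks +/- 1 week later, is taken "if tumor-specific precursor frequency in PBMC is low". Section 9.2.1 does not define low, and does not say which blood draw is used to judge it.

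Four other places list the same second node without the blood condition:
- Section 5.0 describes an optional node sample at the procedure "and again 6 weeks after surgery".
- Section 10.2.1, footnote 8, reads "6 weeks post-surgery only (+/- 1 week").
- Section 10.2.2, footnote 7, says the same for the arm now closed to new patients.
- Section 11.0 has the nodes and tissue form due "6 weeks post-surgical procedure".

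On use of the data, secondary objective 3 in Section 2.2 is "To assess the anti-glioma immune response before and after MK-3475 with MLA". Section 1.6 names the tissues: "Glioma-specific immune response will be assessed in cultured TIL, peripheral blood, and sampled cLN (where available"). Section 15.2 gives the analysis: "Two-group t-test will be used to compare the anti-glioma immune response before and after MK-3475 with or without MLA". It says nothing about pairing, selected samples or missing samples.

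**The concern.** There are two problems, and the second follows only if 9.2.1 is the rule applied.

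First, the documents disagree on who gives the second node. Two sites collect and process their own node samples (9.2.3). They could follow different rules, or apply the same rule with different meanings of low.

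Second, the condition in 9.2.1 selects patients on an immune measure closely related to the one being studied. Section 1.6 treats peripheral blood and lymph node as places where the same glioma-specific response is measured. Using the blood value to decide who contributes a later node, with no such filter on the earlier node, makes the two sets differ for a reason unrelated to treatment. An unpaired test of earlier against later nodes would attribute that difference to treatment. Without a recorded cut-off and deciding draw, the selection could not be reconstructed or adjusted for afterwards.

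**Working it through.** The documents give no sample size, effect size or SD for the node comparison, so there is no planned figure to reproduce. The check is how far the condition alone would move the result when nothing has truly changed.

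**Inputs from the documents.** The condition (9.2.1); the two-group t-test (15.2); 32 patients in the single-arm analysis (15.4) and 20 per group in the older plan (15.1).

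**Assumptions, not in the documents.** Responses are standardised normal. A share q of patients is called low, with q = 1/3, 1/2 or 2/3. The correlation r_A between the deciding blood value and the later node response is 0 to 0.7.

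**Shift in the later mean, unpaired.** Shift = -r_A × φ(z_q)/q, in SD of the node response, where z_q is the normal quantile at q.
- q = 1/2: φ(0)/0.5 = 0.3989/0.5 = 0.798
- q = 1/3: 0.3636/0.3333 = 1.091
- q = 2/3: 0.3636/0.6667 = 0.545

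| Share called low | r_A = 0 | r_A = 0.3 | r_A = 0.5 | r_A = 0.7 |
|---|---|---|---|---|
| 2/3 | 0 | -0.16 | -0.27 | -0.38 |
| 1/2 | 0 | -0.24 | -0.40 | -0.56 |
| 1/3 | 0 | -0.33 | -0.55 | -0.76 |

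**Effect on the t-test.** This was simulated with 4,000 trials per setting and no true change. The earlier and later node responses correlate at 0.5, the blood value correlates half as strongly with the earlier node as with the later one, and every patient gives an earlier node. The two-sided 5% unpaired test, with half called low, rejects as follows:

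| Patients | r_A = 0 | r_A = 0.3 | r_A = 0.5 | r_A = 0.7 |
|---|---|---|---|---|
| 20 | 2.0% | 5.2% | 11.6% | 25.2% |
| 32 | 1.8% | 8.1% | 19.8% | 45.3% |

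Opt-in below 100% would reduce the number analysed, and with it these rejection rates, but not the expected shift.

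**If the analysis is paired within the selected patients.** With r_B the correlation between the blood value and the earlier node, shift = -(r_A - r_B) × φ(z_q)/q. For q = 1/2:
- r_A = 0.3, r_B = 0.15: -0.15 × 0.798 = -0.12 SD
- r_A = 0.7, r_B = 0.35: -0.35 × 0.798 = -0.28 SD
- r_A = 0.25, r_B = 0.5: +0.25 × 0.798 = +0.20 SD

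Pairing halves the shift when r_B is half of r_A. The sign reverses when the blood value follows the earlier node more closely, which is regression to the mean.

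**If the second node is taken regardless of blood.** The simulated bias is 0.00 SD. The paired test rejects in 5.0% to 5.2% of trials and the unpaired test in about 0.5%, because it ignores the pairing.

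**Pairs available.** If all 32 opted in, 32 × 1/2 = 16 or 32 × 1/3 ≈ 11 pairs would remain under the condition.

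**The case against.** The strongest reply is that only the disagreement is established. If Section 5.0, the calendars and the data schedule govern, nothing is selected. Section 5.0 is also permissive about the optional node, so 9.2.1 can be read as the detail behind it, perhaps to spare some patients a second needle aspiration. That stands: the bias is conditional on 9.2.1 being followed. But the disagreement remains, and so does the undefined term.

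It is also fair that neither objective 3 nor the t-test sentence mentions nodes. The link runs through Section 1.6, which lists node as one of three tissues and only where available. Blood is drawn from all phase II patients at fixed times (5.0 and 9.1.1), so a sound before/after test on blood already exists. This limits the harm to the node part.

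A reader might go further and infer three things that the documents do not support:
- **That the later nodes come from weak responders.** Section 9.1.1 schedules blood before the procedure, before dose 1 and before dose 2, and 9.2.1 does not say which draw decides. A pre-treatment draw would select on baseline frequency, not on response.
- **That all patients are compared with a subset.** The earlier nodes also come only from patients who opted in.
- **That the result is biased toward finding no response.** With no true change, the unpaired test would tend to show a spurious decline. Under pairing the bias shrinks or can turn positive, and at zero correlation there is none.

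**Conclusion.** The point holds as an inconsistency with a real selection risk. Section 9.2.1 contradicts four other places on who gives the second node and leaves its own condition undefined. If it is followed, and the two-group test is applied to nodes, the node part of objective 3 is biased whenever the blood value and the node response are correlated.

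Under assumed correlations of 0.3 to 0.7, the unpaired shift in the later mean is -0.24 to -0.56 SD with half of patients called low, and -0.33 to -0.76 SD with a third. These figures illustrate the scale; they are not estimates. The share called low, the correlation, the deciding draw and the pairing are all unknown, and they determine both size and direction. The blood comparison and the primary PFS analysis are not affected. For an optional sample within a secondary objective this is worth correcting, but it does not threaten the trial's main conclusion.

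**What to change.** Reconcile Sections 5.0, 9.2.1, 10.2.1 (footnote 8), 10.2.2 (footnote 7) and 11.0 so that they state one rule. The documents do not show which was intended, so the sponsor must choose.

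- **If the condition is dropped:** the second node stays optional for consenting patients, as 5.0 and 10.2.1 already read. Section 15.2 should compare nodes within patients, using those with both samples.
- **If the condition is kept:** state the blood cut-off and the deciding draw in 9.2.1 and carry the condition into the other four places. Report node results descriptively, in patients with both samples, labelled as a selected subset. Base the formal before/after test for objective 3 on blood. Pairing alone does not remove the selection, so it would not justify a formal node test.

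Either route is a short text amendment and adds no procedure beyond those already described. The cost is small. Dropping the condition means some patients whom 9.2.1 would have spared are offered a second optional aspiration. Keeping it means fewer pairs and less inferential use of the node data.

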9.2.2 Handling of Specimens

Lymph nodes will be minced and cells isolated using a cell strainer per standard protocol (REF). Suspended lymph node lymphocytes will be Ficoll separated and the mononuclear cell population (PBMC) isolated per standard protocol^{37,38}

9.2.3 Shipping of Specimens

Lymph node samples collected at WUSM should be placed in a buffered solution (e.g. PBS, a tissue culture media), transported to and stored in [name]'s lab (located at Couch Biomedical Research Building [name]) at ambient temperature, and processed immediately upon arrival. If a delay in transport or processing of greater than 1 hour is anticipated, samples must be placed on ice. All attempts must be used to process samples within 4 hours of collection.

Lymph node samples collected at UF should be placed a buffered solution (e.g. PBS, a tissue culture media), transported to [name] lab in the

immunophenotyping lab at ambient temperature, and processed immediately upon arrival. If a delay in transport or processing of greater than 1 hour is anticipated, samples must be placed on ice. All attempts must be used to process samples within 4 hours of collection.

9.3 Tumor Tissue Specimens

9.3.1 Collection of Specimens

Any tissue (from either surgical debulking or biopsy or MLA/biopsy) available after histopathologic diagnosis of GBM will be collected for correlated studies as follows:

- Flash frozen for DNA and RNA isolation and for priming of DC
- Fixed and embedded in paraffin for IHC
- Acutely dissociated to generate patients' primary GBM cell lines and tumor infiltrating lymphocyte culture if adequate tissue is available.

Phase II patients will have tissue collected.

Those patients who, in the event of surgical intervention for clinical reasons of a radiographically progressing tumor, undergo a subsequent surgical procedure (whether biopsy or resection) will be collected after histopathologic diagnosis of progressive GBM.

9.3.2 Handling of Specimens

Tissue cryopreservation and paraffin embedding are per standard protocol. One half of the tissue will be equally divided into 2 parts: one part will be flash frozen and the other part will be fixed and embedded in paraffin (FFPE). FFPE samples are to be batch shipped to a MERCK-designated laboratory for central performance of PD-L1 IHC. Five (5) unstained slides may be submitted in lieu of the FFPE tissue block. The other half of the tissue will be divided into 2 parts: one part will be acutely dissociated by digestion with collagenase and hyaluronidase for patient-derived glioma cell line generation, and the other part will be minced into 1 mm chunks then plated for tumor-infiltrating lymphocyte cultures per standard protocol.

9.3.3 Shipping of Specimens

Brain tumor samples collected at WUSM should be placed in a buffered solution (e.g. PBS, a tissue culture media), transported to the laboratory of [name] (3rd floor of McMillan building), or Siteman Cancer Center Tissue Procurement Core at ambient temperature and processed immediately upon arrival. From there the tissue will be divided. The half that will be used for the flash frozen stock and FFPE blocks will be transported and processed in the Siteman Cancer Center's Tissue Procurement Core. The other half that will be used to generate dissociated cells will be delivered immediately to [name] lab (contact person: [name],

[contact]). If a delay in transport or processing of greater than 1 hour is anticipated, samples must be stored on ice. All attempts must be used to process samples within 4 hours of collection.

Brain tumor samples collected at UF should be placed in a buffered solution (e.g. PBS, a tissue culture media), transported to the Florida Center for Brain Tumor Research (FCBTR) tumor bank at UF at ambient temperature and processed immediately upon arrival. From there the tissue will be divided. The half that will be used for the flash frozen stock and FFPE blocks will be processed in the FCBTR. The other half that will be used to generate dissociated cells will be delivered to [name] lab immediately (contact person: [name], [contact]). If a delay in transport or processing of greater than 1 hour is anticipated, samples must be stored on ice. All attempts must be used to process samples within 4 hours of collection.

10.0 STUDY CALENDAR

10.1 Phase I Study Calendar

	Screening	Day 1	Day 2 to Day 8	Q3W ⁹	EOT	Follow-Up ²
H&P, KPS	X		X	X	X	
Brain MRI	X			X ⁴		
CBC	X		X ⁸	X		
CMP ⁷	X		X ⁸	X		
INR, PT/PTT	X					
βhCG ⁶	X		X ⁵			
TSH	X			X ¹		
MK-3475			X	X ³		
MLA		X ⁸				
AE assessment	X	-----				X

1. To be checked at every odd-numbered dose of MK-3475
2. There will be one follow-up visit 4 weeks after EOT, and then patients will be followed for up to 2 years for survival
3. Treatment can continue for a maximum of 2 years/35 cycles after MLA. Patients currently on MK-3475 beyond the 2 year/35 cycle limit at the time of Amendment 13 may remain on MK-3475 unless there is progression, toxicity, or agreement by the patient and PI to discontinue treatment. Refer to Section 5.10 for guidance on whether a patient qualifies for re-treatment in the Second Course Phase and refer to Section 10.3 for the Second Course Phase calendar.
4. Every 9 weeks +/- 1 week
5. No more than 72 hours prior to the first dose. If the screening pregnancy test is performed within that window, only one pregnancy test is required.
6. Women of childbearing potential only
7. CMP consists of albumin, alk phos, ALT, AST, BUN, Ca++, Cl-, CO2, creatinine, glucose, K+, Na+, total bili, total protein
8. Patients will receive peri- and post-operative care as per SOC. This typically includes treatment with steroids and anti-epileptics, repeated neurological exams (approx. hourly in the ICU and approx. every 2 hours in the step-down unit), and draws for CBC and CMP immediately post-MLA and again the following day.

9. +/- 4 days

